## 11. IMMUNOGENICITY

The immunogenicity data, determined by a validated ADA assay (14), will be analyzed with mITT and Per-Protocol populations. The proportion of participants with positive screening assay results and positive confirmation assay results are summarized in [Table 15](#), [Table 16](#), [Table 17](#), and [Table 18](#).

A titer assay will be performed for specimens with detectable ADA (refer to Section 3.3.3 for the definition of detectable ADA). Geometric Mean Titers (GMT) of ADAs will be calculated, along with 95% CIs, for all groups, at each time point ([Table 19](#) and [Table 20](#)). Summaries will also be displayed graphically ([Figure 2](#)).

The GMT is defined as:

$$\text{GMT} = \sqrt[n]{X_1 * X_2 * \dots * X_n},$$

where the  $X_1, X_2, \dots, X_n$  are the titers for each participant at a certain time point for detectable ADAs. In practice, it is the equivalent of:  $\text{GMT} = \text{Exp}\{[\log(X_1) + \log(X_2) + \dots + \log(X_n)] / n\}$

The proportion of participants with detectable ADAs and Clopper-Pearson exact 95% CIs will also be computed over time to assess persistence of ADAs ([Table 21](#) and [Table 22](#)).

The individual ADA results, including screening result, confirmatory result and titers, will be presented in [Listing 10](#).

## **12. OTHER ANALYSES**

Not Applicable.

### **13. REPORTING CONVENTIONS**

The mean, SD, and other statistics will be reported to 1 decimal place greater than the original data. The minimum and maximum will use the same number of decimal places as the original data. Proportions will be presented as 2 decimal places; values greater than zero but <0.01 will be presented as “<0.01”. Percentages will be reported to the nearest whole number; values greater than zero but < 1% will be presented as “<1”; values greater than 99% but less than 100% will be reported as >99%.

Drug concentrations, AUC values, Cmax and their summary statistics will have the same format as the drug concentrations reported by the bioanalytical laboratory. Other PK parameters will be reported to 1 decimal place.

## **14. TECHNICAL DETAILS**

SAS version 9.4 or above will be used to generate all tables, figures and listings.

**15. SUMMARY OF CHANGES IN THE CONDUCT OF THE STUDY OR  
PLANNED ANALYSES**

Not applicable.

## **17. LISTING OF TABLES, FIGURES, AND LISTINGS**

Table, figure, and listing shells are presented in Appendices 1, 2, and 3.

## APPENDICES

---

## 9.1 Overall Study Design and Plan Description

**Table 1: Single Ascending Dose Cohorts and Dose Regimens**

Cohort	Arm	Number of Participants	Study Product
1	1	10	3 mg/kg of EV68-228-N
	2	2	Placebo
2	1	10	10 mg/kg of EV68-228-N
	2	2	Placebo
3	1	10	30 mg/kg of EV68-228-N
	2	2	Placebo

**9.5.1 Immunogenicity and Safety Measurements Assessed and Flow Chart****Table 2: Schedule of Activities**

Study Visit	00	01	02	03	04	05	06	07	08	09	Unscheduled	Early Termination
Study day	-28 to -1	1	2	3	8	15	29	61	91	121		
Visit window ( $\pm$ number of days)					1	2	3	7	14	14		
Procedures												
Informed Consent	X											
Demographic Information	X											
Review Eligibility Criteria	X	X										
Medical History	X											
Concomitant Medications	X	X	X	X	X	X	X				X a	X a
Infusion		X										
Interim Medical History		X	X	X	X	X	X	X	X	X		X
Counsel on avoidance of pregnancy	X	X										
Full Physical Examination	X											
Focused Physical Examination		X	X	X	X						X a	X a
Symptom-driven Physical Examination						X	X	X	X	X		X
Vital Signs	X	X b	X	X	X	X	X				X a	X a
Oximetry Measurement		X b										
Cardiopulmonary Monitoring		X c										
Height and Weight (for BMI calculation)	X											
Weight (for dose calculation)		X										
Hematology d	X	X e	X	X	X		X					X a
Chemistry d	X	X e	X	X	X		X					X a
12-Lead ECG	X	X f	X									
Urine Pregnancy Test g	X	X										
Solicited AEs			Days 1-3									

**Table 2: Schedule of Activities (continued)**

Study Visit	00	01	02	03	04	05	06	07	08	09	Early Termination	
Study day	-28 to -1	1	2	3	8	15	29	61	91	121		
Visit window ( $\pm$ number of days)					1	2	3	7	14	14		
Procedures												
Review e-Memory Aid			X	X	X							
Unsolicited AEs			Days 1-29									
SAEs, MAAEs, and NOCMCs			Days 1-121									
Update previous AE/SAEs (as needed)			X	X	X	X	X	X	X	X	X	
PK samples h		X i	X j	X j	X	X	X	X	X		X	
Serum samples for ADA (anti-drug antibodies) h		X e			X	X	X	X	X		X	
Hypersensitivity Panel Sample k		X k										
Total amount of blood collected for visit (mL)	6	41 or 56 l	11	11	16	10	16	10	10	0	16	
Cumulative blood volume (ml) if there is no hypersensitivity reaction	6	47	58	69	85	95	111	121	131	141		
Cumulative blood volume (mL) if there is a hypersensitivity reaction	6	62	73	84	100	110	126	136	146	156		

a Conducted if visit occurs within 7 days of infusion.b VS will be collected to confirm eligibility prior to randomization and will be repeated, along with oximetry measurements, at approximately 15 minutes prior to infusion, the end of infusion, and at 1-hour post-infusion. For infusions lasting at least 30 minutes, these will also be collected at approximately 15 minutes after the beginning of the infusion.c During infusion and up to one-hour post-infusion, continuous cardio-pulmonary monitoring will be conducted to assess for acute changes. If a CS change occurs, the monitoring will be continued until it has resolved and it is deemed safe to discontinue monitoring by the site PI or designee.d Clinical screening laboratory evaluations will include WBCs, Hgb, PLT, Cr, ALT, and T. Bili. Clinical safety laboratory evaluations obtained on Days 1, 2, 3, 8, and 29 will include WBCs, Hgb, PLTs, Cr, ALT, and T. Bili. Results of laboratory studies collected prior to infusion on Day 1 do not require review prior to infusion; rather, they serve as a baseline assessment for post-infusion safety assessment.e Day 1 blood draws for ADA, hematology and chemistry should be done at the same time as the first PK blood draw, within 15 minutes prior to the infusion.f ECGs on Day 1 will occur approximately 15 minutes prior to infusion and 1-hour post-infusion.g For women of childbearing potential, a urine pregnancy test at screening and on Day 1 with results confirmed as negative prior to infusion.h If an infusion is terminated early, the remaining Day 1 PK samples will not be drawn and the PK and ADA samples at follow-up visits will not be drawn.i PK samples on Day 1 will be obtained approximately 15 minutes prior to infusion, at end of infusion (within a  $\pm$  5-minute window), and at 1-, 3-, and 5-hours post end of infusion, within a  $\pm$  15-minute window. Note, for infusions that last longer than 1-hour due to infusion related events or other disruptions in administration, see MOP for details on updating the PK collection timepoints.j PK sample will be collected within  $\pm$ 3-hour window of 24- and 48-hours after the end of infusion.k All participants will have a baseline sample taken for hypersensitivity testing approximately 15 minutes prior to infusion. For any participant that has an anaphylactic or anaphylactoid-type reaction, three additional samples will be taken: 1) at the onset of symptoms, 2) at 2 or more hours after onset, 3) at the resolution of symptoms.l Larger amount will be collected only if there is a hypersensitivity reaction.

### 9.7.1 Sample Size

**Table 3: Probability to Observe at Least n AEs Within Study Population**

Adverse Event Probability	Probability to Observe At Least n AEs									
	n=1	n=2	n=3	n=4	n=5	n=6	n=7	n=8	n=9	n=10
5%	40.1%	8.6%	1.2%	0.1%	0.0%	0.0%	0.0%	0.0%	0.0%	0.0%
10%	65.1%	26.4%	7.0%	1.3%	0.2%	0.0%	0.0%	0.0%	0.0%	0.0%
15%	80.3%	45.6%	18.0%	5.0%	1.0%	0.1%	0.0%	0.0%	0.0%	0.0%
20%	89.3%	62.4%	32.2%	12.1%	3.3%	0.6%	0.1%	0.0%	0.0%	0.0%
25%	94.4%	75.6%	47.4%	22.4%	7.8%	2.0%	0.4%	0.0%	0.0%	0.0%
30%	97.2%	85.1%	61.7%	35.0%	15.0%	4.7%	1.1%	0.2%	0.0%	0.0%

## 10.2 Protocol Deviations

**Table 4: Distribution of Protocol Deviations by Category, Type, and Dose Cohort – All Enrolled Participants**

[Implementation notes: Only include deviation categories/types that exist in the data, if there are none in some category/type then delete the row. ]

Category	Deviation Type	3 mg/kg EV68-228-N (N=X)		10 mg/kg EV68-228-N (N=X)		30 mg/kg EV68-228-N (N=X)		Placebo (N=X)		All Participants (N=X)	
		No. of Pts.	No. of Dev.	No. of Pts.	No. of Dev.	No. of Pts.	No. of Dev.	No. of Pts.	No. of Dev.	No. of Pts.	No. of Dev.
Major Deviation											
Eligibility/Enrollment	Any type										
	Did not meet inclusion criterion	X	X	X	X	X	X	X	X	X	X
	Met exclusion criterion										
	Other										
Informed Consent/Assent	Any Type										
	ICF not signed prior to study procedures										
	Incorrect version of ICF signed										
	Unapproved consent/reconsent informed consent method used										
Product administration schedule	Any type										
	Out of window visit										
	Missed visit/visit not conducted										
	Missed treatment administration										
	Delayed treatment administration										
	Other										
Follow-up visit schedule	Any type										
	Out of window visit										
	Missed visit/visit not conducted										
	Other										
Protocol procedure/assessment	Any type										
	Required procedure not conducted										
	Required procedure done incorrectly										

**Table 4: Distribution of Protocol Deviations by Category, Type, and Dose Cohort (continued)**

Category	Deviation Type	3 mg/kg EV68-228-N (N=X)		10 mg/kg EV68-228-N (N=X)		30 mg/kg EV68-228-N (N=X)		Placebo (N=X)		All Participants (N=X)	
		No. of Pts.	No. of Dev.	No. of Pts.	No. of Dev.	No. of Pts.	No. of Dev.	No. of Pts.	No. of Dev.	No. of Pts.	No. of Dev.
	Safety Lab not Collected										
	Other										
Laboratory/Specimen	Any type										
	Specimen result not obtained										
	Conduct of Non-Protocol Procedure										
	Specimen Processing not conducted correctly										
	Specimen Temperature Excursion										
	Other										
Product Storage	Any type										
	Study Product Temperature Excursion										
	Other										
Safety	Any type										
	Safety Lab not Collected										
	Required procedure done incorrectly										
	Required procedure not conducted										
	Specimen result not obtained										
	Other										
Repeat for Minor Deviations											
Repeat for All Deviations											

Note: N=Number of participants enrolled in each group.

### 12.4.1 Individual Laboratory Measurements and Abnormal Laboratory Values

**Table 5: Laboratory Adverse Event Grading Scale**

Protocol Assessment	Grade 1	Grade 2	Grade 3	Grade 4
Hematology				
Hemoglobin, Low (male) g/dL	12.0 - 13.0	10.0 - 11.9	8.0 - 9.9	<8.0
Hemoglobin, Low (female) g/dL	10.5 - 11.5	9.0 - 10.4	7.5 - 8.9	<7.5
WBC, Low mm 	2,500 - 2,999	1,500 - 2,499	1,000 - 1,499	<1,000
WBC, High mm 	11,600 - 15,000	15,001 - 20,000	20,001 - 25,000	>25,000
Platelets (Decrease) mm 	125,000 - 139,000	100,000 - 124,000	25,000 - 99,000	<25,000
Chemistry				
ALT	2.0 - 3.5x ULN	>3.5 - 5.0x ULN	>5.0 - 10x ULN	>10x ULN
Creatinine	1.5 - 1.7x ULN	>1.7 - 2.0x ULN	>2.0 - 2.5x ULN	>2.5x ULN or requires dialysis
Bilirubin	1.5 - 2.0x ULN	>2.0 - 3.0x ULN	>3.0 - 5.0x ULN	>5.0x ULN
Vital Signs				
Hypertension (systolic) mmHg	141 - 150	151 - 155	>155	ER visit or hospitalization for management
Hypertension (diastolic) mmHg	91 - 95	96 - 100	>100	ER visit or hospitalization for management
Hypotension (systolic) mmHg	85-89	80-84	<80	ER visit or hospitalization for management
Bradycardia, baseline >60 bpm	50 - 54	45-49	<45	ER visit or hospitalization for management
Bradycardia, baseline <60 bpm	45-50	40-44	<40	ER visit or hospitalization for management
Tachycardia bpm	101 - 115	116 - 130	>130	ER visit or hospitalization for management
Temperature °C	38.0 - 38.4	38.5 - 38.9	39.0 - 40.0	>40

## 14.1 Description of Study Participants

### 14.1.1 Disposition of Participants

**Table 6: Participant Disposition by Dose Cohort – All Enrolled Participants**

Participant Disposition	3 mg/kg EV68-228-N (N=X)		10 mg/kg EV68-228-N (N=X)		30 mg/kg EV68-228-N (N=X)		Placebo (N=X)		All Participants (N=X)	
	n	%	n	%	n	%	n	%	n	%
Screened	--	--	--	--	--	--	--	--	x	--
Enrolled/Randomized	x	100	x	100	x	100	x	100	x	100
Received Treatment	x	xx	x	xx	x	xx	x	xx	x	xx
Completed Final Blood Draw for Safety at Study Day 29	x	xx	x	xx	x	xx	x	xx	x	xx
Completed at Least One Post-Dose Blood Draw for PK	x	xx	x	xx	x	xx	x	xx	x	xx
Completed Final Blood Draw for ADA at Study Day 121	x	xx	x	xx	x	xx	x	xx	x	xx
Terminated from the study follow-up	x	xx	x	xx	x	xx	x	xx	x	xx
Completed Follow-up (Study Day 121) a	x	xx	x	xx	x	xx	x	xx	x	xx
Completed Per Protocol b	x	xx	x	xx	x	xx	x	xx	x	xx

Note: N=Number of participants enrolled in each group.

a Refer to Listing 16.2.1 for reasons participants discontinued or terminated early.

b Refer to Listing 16.2.3 for reasons participants are excluded from the Analysis populations.

**Table 7: Analysis Populations by Dose Cohort – All Enrolled Participants**

Analysis Populations	Reason Participants Excluded	3 mg/kg EV68-228-N (N=X)		10 mg/kg EV68-228-N (N=X)		30 mg/kg EV68-228-N (N=X)		Placebo (N=X)		All Participants (N=X)	
		n	%	n	%	n	%	n	%	%	n
Safety Population	Any Reason	x	xx	x	xx	x	xx	x	xx	x	xx
	[Reason 1, for example: Did not receive study product]										
mITT Population	Any Reason										
	Did not receive at least a partial study product										
	Did not have a valid pre-dose immunogenicity testing result										
	Did not have any valid post-dose immunogenicity testing result										
Per-Protocol Population	Any Reason										
	Excluded from mITT										
	Found to be ineligible at baseline.										
	[Reason 3]										
	[Reason 4]										
Pharmacokinetics Population	Any Reason										
	Did not receive a full dose of study product.										
	Do not have at least one evaluable serum PK samples for the estimation of $C_{max}$ OR $AUC_{0-\infty}$										
	[Reason 3]										
	[Reason 4]										

Note: N=Number of participants enrolled in each group.

**Table 8: Dates of Treatment by Site and Dose Cohort**

[Implementation Note: The dates of dosing will be categorized by 3 months period (from first enrollment in each cohort).]

Dates of Dosing	University of Maryland EV68-228-N (N=X)	University of Maryland Placebo (N=X)	Vanderbilt University EV68-228-N (N=X)	Vanderbilt University Placebo (N=X)	All Sites EV68-228-N (N=X)	All Sites Placebo (N=X)	All Sites All Participants (N=X)
Total (Entire period of enrollment)							
Cohort 1							
DDMMYYYY-DDMMYYYY [categorize based on length of enrollment period]	x	x	x	x	x	x	x
Cohort 2							
DDMMYYYY-DDMMYYYY [categorize based on length of enrollment period]	x	x	x	x	x	x	x
Cohort 3							
DDMMYYYY-DDMMYYYY [categorize based on length of enrollment period]	x	x	x	x	x	x	x

Note: N=Number of participants enrolled in each group.

**Table 9: Ineligibility Summary of Screen Failures**

Inclusion/Exclusion Category	Inclusion/Exclusion Criterion	n a	% b
Inclusion and Exclusion	Number of participants failing any eligibility criterion	x	100
Inclusion	Any inclusion criterion	x	xx
	[inclusion criterion 1]	x	xx
	[inclusion criterion 2]	x	xx
	[inclusion criterion 3]	x	xx
Exclusion	Any exclusion criterion	x	xx
	[exclusion criterion 1]	x	xx
	[exclusion criterion 2]	x	xx
	[exclusion criterion 3]	x	xx
Eligible but not enrolled		x	-

a More than one criterion may be marked per participant.b Denominator for percentages is the total number of screen failures.

### 14.1.2 Demographic Data by Study Group

**Table 10: Summary of Categorical Demographic and Baseline Characteristics by Site**

Variable	Characteristic	University of Maryland (N=X)		Vanderbilt University (N=X)		All Participants (N=X)	
		n	%	n	%	n	%
Sex	Male	x	xx	x	xx	x	xx
	Female						
Ethnicity	Not Hispanic or Latino	x	xx	x	xx	x	xx
	Hispanic or Latino						
	Not Reported						
Race	Unknown						
	American Indian or Alaska Native	x	xx	x	xx	x	xx
	Asian						
	Native Hawaiian or Other Pacific Islander						
	Black or African American						
	White						
	Multi-Racial						
	Unknown						

Note: N=Number of participants enrolled in each site.

**Table 11: Summary of Continuous Demographic and Baseline Characteristics by Site**

Variable	Statistic	University of Maryland (N=X)	Vanderbilt University (N=X)	All Participants (N=X)
Age (yrs)	Mean (SD)	xx.x (xx.x)	xx.x (xx.x)	xx.x (xx.x)
	Median (min, max)	xx.x (x.x, x.x)	xx.x (x.x, x.x)	xx.x (x.x, x.x)
Height (cm)	Mean (SD)	xx.x (xx.x)	xx.x (xx.x)	xx.x (xx.x)
	Median (min, max)	xx.x (x.x, x.x)	xx.x (x.x, x.x)	xx.x (x.x, x.x)
Weight (kg)	Mean (SD)	xx.x (xx.x)	xx.x (xx.x)	xx.x (xx.x)
	Median (min, max)	xx.x (x.x, x.x)	xx.x (x.x, x.x)	xx.x (x.x, x.x)
BMI (kg/m  )	Mean (SD)	xx.x (xx.x)	xx.x (xx.x)	xx.x (xx.x)
	Median (min, max)	xx.x (x.x, x.x)	xx.x (x.x, x.x)	xx.x (x.x, x.x)

Notes: N=Number of participants enrolled in each site.

BMI is calculated with the height obtained at screening and the weight obtained at Day 1 prior dosing.

**Table 12: Summary of Categorical Demographic and Baseline Characteristics by Dose Cohort – All Enrolled Participants**

Variable	Characteristic	3 mg/kg EV68-228-N (N=X)		10 mg/kg EV68-228-N (N=X)		30 mg/kg EV68-228-N (N=X)		Placebo (N=X)		All Participants (N=X)	
		n	%	n	%	n	%	n	%	n	%
Sex	Male	x	xx	x	xx	x	xx	x	xx	x	xx
	Female										
Ethnicity	Not Hispanic or Latino	x	xx	x	xx	x	xx	x	xx	x	xx
	Hispanic or Latino										
	Not Reported										
	Unknown										
Race	American Indian or Alaska Native	x	xx	x	xx	x	xx	x	xx	x	xx
	Asian										
	Native Hawaiian or Other Pacific Islander										
	Black or African American										
	White										
	Multi-Racial										
	Unknown										

Note: N=Number of participants enrolled in each group.

**Table 13: Summary of Continuous Demographic and Baseline Characteristics by Dose Cohort – All Enrolled Participants**

Variable	Statistic	3 mg/kg EV68-228-N (N=X)	10 mg/kg EV68-228-N (N=X)	30 mg/kg EV68-228-N (N=X)	Placebo (N=X)	All Participants (N=X)
Age (yrs)	Mean (SD)	xx (xx)	xx (xx)	xx (xx)	xx (xx)	xx (xx)
	Median (min, max)	xx.x (xx.x, xx.x)	xx.x (xx.x, xx.x)	xx.x (xx.x, xx.x)	xx.x (xx.x, xx.x)	xx.x (xx.x, xx.x)
Height (cm)	Mean (SD)	xx (xx)	xx (xx)	xx (xx)	xx (xx)	xx (xx)
	Median (min, max)	x (x, x)	x (x, x)	x (x, x)	x (x, x)	x (x, x)
Weight (kg)	Mean (SD)	xx (xx)	xx (xx)	xx (xx)	xx (xx)	xx (xx)
	Median (min, max)	x (x, x)	x (x, x)	x (x, x)	x (x, x)	x (x, x)
BMI (kg/m  )	Mean (SD)	xx (xx)	xx (xx)	xx (xx)	xx (xx)	xx (xx)
	Median (min, max)	x (x, x)	x (x, x)	x (x, x)	x (x, x)	x (x, x)

Notes: N=Number of participants enrolled in each group.

BMI is calculated with the height obtained at screening and the weight obtained at Day 1 prior dosing.

### 14.1.3 Prior and Concurrent Medical Conditions

**Table 14: Summary of Participants with Pre-Existing Medical Conditions by MedDRA System Organ Class, Preferred Term and Dose Cohort**

MedDRA System Organ Class	MedDRA Preferred Term	3 mg/kg EV68-228-N (N=X)		10 mg/kg EV68-228-N (N=X)		30 mg/kg EV68-228-N (N=X)		Placebo (N=X)		All Participants (N=X)	
		n	%	n	%	n	%	n	%	n	%
Any SOC	Any PT	x	xx	x	xx	x	xx	x	xx	x	xx
[SOC 1]	Any PT										
	PT1										
	PT2										
[SOC 2]	Any PT										
	PT1										
	PT2										

Notes: N=Number of participants enrolled in each group; n=Number of participants reporting medical history within the specified SOC and PT. A participant is only counted once per SOC and per PT.

## 14.2 Immunogenicity Data

**Table 15: Proportion of Participants with a Positive Screening Assay by Time Point and Dose Cohort – mITT Population**

Time Point	3 mg/kg EV68-228-N (N=X)		10 mg/kg EV68-228-N (N=X)		30 mg/kg EV68-228-N (N=X)		Placebo (N=X)		All Participants (N=X)	
	n	%	n	%	n	%	n	%	n	%
Day 1, Pre Dose	x	xx	x	xx	x	xx	x	xx	x	xx
Day 8										
Day 15										
Day 29										
Day 61										
Day 91										
Day 121										

Note: N=Number of participants in each group in the mITT Population.

Table with similar format:

**Table 16: Proportion of Participants with a Positive Screening Assay by Time Point and Dose Cohort – Per-Protocol Population**

**Table 17: Summary of Positive ADA Confirmation Assay Results by Time Point and Dose Cohort – mITT Population**

[Implementation note, if there is number of participants with positive Screening result is N=0, then the cell will be ‘-’.]

Time Point	3 mg/kg EV68-228-N	10 mg/kg EV68-228-N	30 mg/kg EV68-228-N	Placebo	All Participants
	n/N	n/N	n/N	n/N	n/N
Day 1, Pre Dose	x/X	x/X	x/X	x/X	x/X
Day 8					
Day 15					
Day 29					
Day 61					
Day 91					
Day 121					

Notes: N=Number of participants with positive screening results in each group in the mITT Population.

n=Number of participants with positive confirmation results in each group in the mITT Population

Table with similar format:

**Table 18: Summary of Positive ADA Confirmation Assay Results by Time Point and Dose Cohort – Per-Protocol Population**

**Table 19: Anti-Drug Antibodies (ADA) Geometric Mean Titer (GMT) Results with 95% Confidence Intervals by Time Point and Dose Cohort – mITT Population**

Time Point	Statistic	3 mg/kg EV68-228-N	10 mg/kg EV68-228-N	30 mg/kg EV68-228-N	Placebo
Day 1, Pre Dose	N	x	x	x	x
	GMT	x.x	x.x	x.x	x.x
	95% CI	x.x, x.x	x.x, x.x	x.x, x.x	x.x, x.x
Day 8	N				
	GMT				
	95% CI				
Day 15	N				
	GMT				
	95% CI				
Day 29	N				
	GMT				
	95% CI				
Day 61	N				
	GMT				
	95% CI				
Day 91	N				
	GMT				
	95% CI				
Day 121	N				
	GMT				
	95% CI				

Note: N=Number of participants in each group in the mITT Population.

**Table 20: Anti-Drug Antibodies (ADA) Geometric Mean Titer (GMT) Results with 95% Confidence Intervals by Time Point and Dose Cohort – Per-Protocol Population**

Time Point	Statistic	3 mg/kg EV68-228-N (N=X)	10 mg/kg EV68-228-N (N=X)	30 mg/kg EV68-228-N (N=X)	Placebo (N=X)
Day 1, Pre-Dose	N	x	x	x	x
	GMT	x.x	x.x	x.x	x.x
	95% CI	x.x, x.x	x.x, x.x	x.x, x.x	x.x, x.x
Day 8	N				
	GMT				
	95% CI				
Day 15	N				
	GMT				
	95% CI				
Day 29	N				
	GMT				
	95% CI				
Day 61	N				
	GMT				
	95% CI				
Day 91	N				
	GMT				
	95% CI				
Day 121	N				
	GMT				
	95% CI				

Note: N=Number of participants in each group in the Per-Protocol Population.

**Table 21: Proportion of Participants with Detectable Anti-Drug Antibodies (ADA) with 95% Confidence Intervals by Time Point and Dose Cohort – mITT Population**

[Implementation note: the Detectable Anti-Drug Antibodies means that in the confirmatory ADA assays, the results are positive.]

Time Point	Statistics	3 mg/kg EV68-228-N	10 mg/kg EV68-228-N	30 mg/kg EV68-228-N	Placebo
Any time point	N	x	x	x	x
	n	x	x	x	x
	Proportion (95% CI)	x (x.xx, x.xx)	x (x.xx, x.xx)	x (x.xx, x.xx)	x (x.xx, x.xx)
Day 1, Pre Dose	N	x	x	x	x
	n				
	Proportion (95% CI)				
Day 8	N	x	x	x	x
	n				
	Proportion (95% CI)				
Day 15	N	x	x	x	x
	n				
	Proportion (95% CI)				
Day 29	N	x	x	x	x
	n				
	Proportion (95% CI)				
Day 61	N	x	x	x	x
	n				
	Proportion (95% CI)				
Day 121	N	x	x	x	x
	n				
	Proportion (95% CI)				

Note: N=Number of participants in each group at the time point in the mITT Population.

**Table 22: Proportion of Participants with Detectable Anti-Drug Antibodies (ADA) with 95% Confidence Intervals by Time Point and Dose Cohort – Per-Protocol Population**

[Implementation note: the Detectable Anti-Drug Antibodies means that in the confirmatory ADA assays, the results are positive.]

Time Point	Statistics	3 mg/kg EV68-228-N	10 mg/kg EV68-228-N	30 mg/kg EV68-228-N	Placebo
Any time point	N	x	x	x	x
	n	x	x	x	x
	Proportion (95% CI)	x (x.xx, x.xx)	x (x.xx, x.xx)	x (x.xx, x.xx)	x (x.xx, x.xx)
Day 1, Pre Dose	N	x	x	x	x
	n				
	Proportion (95% CI)				
Day 8	N	x	x	x	x
	n				
	Proportion (95% CI)				
Day 15	N	x	x	x	x
	n				
	Proportion (95% CI)				
Day 29	N	x	x	x	x
	n				
	Proportion (95% CI)				
Day 61	N	x	x	x	x
	n				
	Proportion (95% CI)				
Day 121	N	x	x	x	x
	n				
	Proportion (95% CI)				

Note: N=Number of participants in each group at the time point in the Per-Protocol Population.

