##### **3.1.2. Secondary**

- To characterize the PK of single ascending doses of EV68-228-N for approximately four months following the infusion.
- To measure the occurrence of Anti-Drug Antibodies (ADAs) elicited following a single IV infusion of EV68-228-N in healthy adults.

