##### **3.2.2. Secondary**

After a single IV infusion of EV68-228-N:

- EV68-228-N concentrations in serum will be determined with a validated assay. The PK parameters will be estimated based on the concentration-time data, including area under the serum concentration-time curve (AUC) from time 0 to infinity ( $AUC_{0-\infty}$ ), AUC from time 0 to 48 hours post dose ( $AUC_{0-48}$ ), AUC from time 0 to the time of the last quantifiable concentration ( $AUC_{0-\text{last}}$ ), maximum observed serum concentration ( $C_{\max}$ ), time of the  $C_{\max}$  ( $T_{\max}$ ), apparent serum terminal elimination half-life ( $t_{1/2}$ ), total serum clearance (CL), and volume of distribution during the terminal phase ( $V_z$ ) calculated from serum EV68-228-N levels.
- Incidence of anti-EV68-228-N antibodies as measured by the proportion of participants with detectable anti-EV68-228-N antibodies in serum.

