### 3.3.3. Detectable Anti-Drug Antibody

There are three steps in the Meso Scale Discovery (MSD) Electrochemiluminescent (ECL) assay: screening assay, confirmatory assay, and titer assay. The screening assay will have qualitative results of negative (NEG), potential positive screening (PPS) and no recorded result (NRR).

An ADA confirmatory assay will be performed for specimens with PPS screening results. The result of the confirmatory assay is qualitative, NEG, NRR, or positive (POS).

A detectable ADA is defined when the confirmatory assay result is POS.

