Following informed consent, participants will be screened for eligibility, including medical history, physical examination, weight and height measurements, VS, screening laboratory tests, and a 12-lead ECG. Within 28 days of screening, eligible participants will be seen at the clinical research unit (Day 1) and be randomized to receive either a single IV dose of EV68-228-N or placebo (formulation buffer alone). Participants will remain in the unit for at least 5 hours following infusion and return for assessments on Day 2 and Day 3. Participants will have subsequent follow-up clinic visits on Days 8, 15, 29, 61, 91, and 121.

Participants will be monitored and assessed for safety and the incidence of AEs at all visits beginning with the dosing visit. An electronic memory aid will be utilized from Day 1 through Day 3 to assist with collecting solicited AEs. Safety laboratory studies will be collected at screening and on Days 1, 2, 3, 8, and 29. Concomitant medications taken 28 days before and after dosing will be recorded.

PK samples will be collected prior to infusion, at the end of infusion, at 1, 3, 5, 24 and 48 hours after end of infusion; and on Days 8, 15, 29, 61, 91, and 121. The single dose PK parameters to be estimated include  $C_{max}$ ,  $T_{max}$ , -  $AUC_{0-48}$ ,  $AUC_{0-last}$ , and  $AUC_{0-\infty}$ ,  $t_{1/2}$ , CL, and Vz. PK parameters will be calculated from serum EV68-228-N levels measured using a validated ECL assay performed by PPD, Inc..

Samples for serum levels of anti-EV68-228-N antibodies will be collected prior to infusion on Day 1 and on Days 8, 15, 29, 61, 91 and 121.

A sample will be collected pre-infusion on Day 1 for hypersensitivity testing in the event that the participant experiences an infusion reaction. These baseline samples will only be analyzed in the event of a hypersensitivity reaction related to the infusion. If a participant experiences anaphylaxis or an anaphylactoid event related to the infusion, three additional samples will be collected: 1) during onset, 2) 2 or more hours after onset, and 3) after resolution of symptoms.

The study dosing plan is shown in [Table 1](#).

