#### 4.5.2. Immunogenicity Variables

In this study, the immunogenicity data are measuring the anti-drug response. A validated ECL assay will be performed on samples collected approximately within 15 minutes prior to the infusion on Day 1 and at Days 8, 15, 29, 61, 91 and 121 (with corresponding windows) for serum levels of anti-EV68-228-N antibodies. To measure ADA, anti-drug antibodies will be captured by EV68-228-N and detected with labeled EV68-228-N (e.g., biotin) followed by standard detection (e.g., streptavidin -SULFO-TAG).

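### Tables 21 and 22: the only cross-visit ADA row is not limited to post-dose samples, and Day 91 has no row

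*SAP*

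**What the plan says.** The secondary objective in SAP Section 3.1.2 is "To measure the occurrence of Anti-Drug Antibodies (ADAs) elicited following a single IV infusion of EV68-228-N in healthy adults". The matching outcome measure in Section 3.2.2 stands under the stem "After a single IV infusion of EV68-228-N" and reads "Incidence of anti-EV68-228-N antibodies as measured by the proportion of participants with detectable anti-EV68-228-N antibodies in serum".

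Section 3.3.3 sets the rule for a positive: "A detectable ADA is defined when the confirmatory assay result is POS". The implementation notes to Tables 21 and 22 repeat it: "the Detectable Anti-Drug Antibodies means that in the confirmatory ADA assays, the results are positive". Neither place adds a condition on timing or on change from baseline.

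Section 4.1 states that ADA samples "will be collected prior to infusion on Day 1 and on Days 8, 15, 29, 61, 91 and 121". Section 4.5.2 gives the same post-dose schedule: "at Days 8, 15, 29, 61, 91 and 121 (with corresponding windows) for serum levels of anti-EV68-228-N antibodies".

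Section 11 assigns to Tables 21 and 22 the detectable-ADA proportion with a Clopper-Pearson 95% CI over time, to show persistence. Both shells open with a row labelled "Any time point", followed by the Day 1 pre-dose row and rows for Days 8, 15, 29, 61 and 121. The footnotes define N at each time point and do not define the opening row.

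**The concern.** The objective and the outcome measure are post-dose quantities. The opening row of the two tables is not limited to post-dose samples, and the pre-dose visit is one of the listed time points. A programmer who follows the shell would count a participant whose only confirmed positive came before dosing. No other planned display gives a per-participant proportion across visits: Tables 15 to 20 and Figure 2 are by time point, and Listing 10 is by sample. With 10 participants per dose and 6 on placebo, one such count is visible in the summary.

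The missing Day 91 row has two consequences. The persistence series jumps from Day 61 to Day 121. And since Day 91 is not among the listed time points, it is unclear whether the summary row takes it in; if it does not, a participant positive only at Day 91 is missed.

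**Working it through.** **1. Timing.** Objective: elicited after infusion. Outcome measure: after infusion. Positive: any confirmed result, at any time. Summary row: no timing limit, with a pre-dose row directly beneath it. Under the mITT definition (Section 6.3.1) everyone in Table 21 has a valid pre-dose result, so anyone could contribute a pre-dose-only positive.

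**2. The SAP's own practice.** In the laboratory and vital-sign shells (for example Tables 44 and 68) the cross-visit row is labelled and footnoted as post-baseline. Tables 21 and 22 lack that qualifier.

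**3. Visits.** Scheduled post-dose ADA visits {8, 15, 29, 61, 91, 121} minus the post-dose rows of Tables 21 and 22 {8, 15, 29, 61, 121} leaves {91}. One of six post-dose visits has no proportion or CI in either table. Tables 15, 17, 19 and 20 all have a Day 91 row.

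**4. Effect of one participant.** Group sizes (10 per dose, 6 placebo) are from Section 5. The Clopper-Pearson bounds are:
- 0/n: upper bound 1 - 0.025^(1/n), which is 0.3085 for n = 10 and 0.4593 for n = 6.
- 1/n: lower bound 1 - 0.975^(1/n), which is 0.0025 for n = 10 and 0.0042 for n = 6. The upper bound solves P(X ≤ 1) = 0.025, giving 0.4450 and 0.6412.

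One pre-dose-only positive therefore moves a dose group from 0/10 (0-31%) to 1/10 (0.3-44.5%), and placebo from 0/6 (0-46%) to 1/6 (0.4-64%). One Day-91-only positive left out of the row produces the same shift in the other direction.

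**5. How likely.** The SAP gives no pre-dose positive rate, so this step is assumption only. Let p be that rate and f the share of pre-dose positives who are negative at every later visit. The chance of at least one pre-dose-only positive is 1 - (1 - pf)^n. For p = 1%, 2%, 5%, 10%:
- f = 0: zero throughout.
- f = 0.5: 4.9%, 9.6%, 22.4%, 40.1% for n = 10; 3.0%, 5.9%, 14.1%, 26.5% for n = 6.
- f = 1 (upper bound): 9.6%, 18.3%, 40.1%, 65.1% for n = 10; 5.9%, 11.4%, 26.5%, 46.9% for n = 6.

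**6. What can be recovered for Day 91.** Table 17 gives the confirmed positives, but its N is the number who screened positive. Table 15 gives n and % for positive screens. Section 6.1 bases percentages on the non-missing sample size, so the number tested can usually be worked back when n is above zero: n = 1 shown as 11% implies 1/0.11, about 9 tested. If nobody screens positive, the proportion is 0. Listing 10 holds the sample-level results. The planned proportion with its CI is still not printed.

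**The case against.** The strongest reply is that the row is an ambiguous label, not a wrong analysis. Sections 3.1.2 and 3.2.2 already limit the quantity to post-dose samples, a sensible programmer would apply that limit, and the pre-dose row printed beneath shows any baseline positives. Section 11 never mentions a cross-visit row. Day 91 results are collected, listed and shown in sister tables, Section 11 excludes no visit, and Section 1 describes the shells as samples.

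Much of this stands, and it limits the weight. It does not remove the point. The shell is what gets programmed, the SAP qualifies the equivalent rows elsewhere, and nothing in the document gives a reason to drop Day 91 from the tables meant to show persistence.

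Three stronger readings are tempting and are not supported:
- A reader might infer that the secondary endpoint estimate is wrong. The SAP does not name this row as the endpoint estimate; it is only the sole cross-visit proportion planned.
- A reader might infer that Day 91 data are lost, or can be rebuilt only from Listing 10. Under the Section 6.1 denominator rule, Tables 15 and 17 usually give the proportion.
- A reader might infer that correcting the row can only lower the count. That fails if the row as it stands leaves out Day 91: removing pre-dose samples can lower the count, and including Day 91 can raise it.

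**Conclusion.** Both defects are in the shells. The summary row, as labelled, admits pre-dose-only positives and so does not match the objective or the outcome measure. Day 91 is missing from both tables, and its place in the summary row is undefined. The weight is minor: the endpoint is secondary and descriptive, no sample size or error rate depends on it, and a reader could correct the figures by hand from Listing 10. The absence of Day 91 and of the post-dose qualifier is certain from the text. The size of any distortion is not: it is nil if no one is positive only pre-dose and no one is positive only at Day 91, and one participant of either kind shifts a dose group by 10 percentage points (1/10) or placebo by about 17 (1/6).

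**What to change.** In both Table 21 and Table 22:
- Relabel the summary row as any post-dose time point (Days 8-121, including Day 91).
- Keep the Day 1 pre-dose row as it is.
- Add a Day 91 row with N, n, proportion and exact 95% CI.
- Footnote N for the summary row as participants in that population with at least one retained valid post-dose result. In Table 21 this is the mITT count (Section 6.3.1); in Table 22 it follows the visit-level exclusions of Section 6.3.2.

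Optionally, add a treatment-emergent row (negative before dosing, confirmed positive afterwards). Relabelling alone does not separate elicited antibodies from pre-existing reactivity that persists.

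The cost is one label, one row and one footnote in each of two shells, using results already planned for collection. Making the change before results are seen avoids a post hoc choice of rule.
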